## 9. STATISTICAL CONSIDERATIONS

### 9.1 Analysis Plan

The primary study endpoint is to compare the change in breast density as measured by FWR-MRI (when measured at baseline, 6 and 12 months) between metformin and placebo groups. Additional endpoints such as systemic hormone and cytokines, body weight, waist circumference, and waist-hip ratio will be measured at baseline, 6 and 12 months. Analysis for all study endpoints will be based on a linear mixed-effects model for the observed values across time, to adjust for the correlation among measurements within the same woman. The main effects in the model will be time (0, 6, 12), treatment group (metformin versus placebo), and the interaction between time and treatment group. The time parameter tests if there is a change among placebo treated women, while the group-by-time interaction tests if the change in metformin treated women differs from that in the placebo group. We expect that a simpler covariance structure, such as compound symmetry, will be adequate for repeated measurements within the same woman (since the measurements are equally spaced). Alternatively, we will compare correlation structures for the longitudinal measurements using Akaike's information criterion. All endpoints will be first assessed for normality, and transformations (such as a logarithmic transformation) will be used as necessary to reduce skewness prior to statistical analysis.

Secondary analyses will assess whether differences in the changes in FWR-MRI between the metformin and placebo groups remain after adjustment for potential explanatory variables, such as changes in body weight, systemic hormones, and cytokines. These explanatory variables will be added as independent predictors in the linear mixed-effects models. These analyses will be restricted to explanatory variables that have demonstrated statistically significant metformin effects across time.

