For the metabolomic aim, pre- to post-intervention changes in all detectable compounds of known identity (currently comprising 397 biochemicals using the standard platforms offered by Metabolon, Inc) will be determined and compared between treatment groups using a two-sample t-test. An estimate of the false discovery rate ( $q$ -value) will be calculated (115) to take into account the multiple comparisons that normally occur in metabolomic-based studies. A low  $q$ -value ( $q \leq 0.10$ ) is an indication of high confidence in a result. While a higher  $q$ -value indicates diminished confidence, it does not necessarily rule out the significance of a result. Other lines of evidence may be taken into consideration when determining whether a result merits further scrutiny. Such evidence may include a) significance in another dimension of the study, b) inclusion in a common pathway with a highly significant compound, or c) residing in a similar functional biochemical family with other significant compounds.

Exploratory analyses will assess whether the observed metformin-induced changes in metabolite features are correlated with changes in FWR-MRI, body weight/composition, systemic hormones, and cytokines. The correlation will be estimated using a Pearson correlation coefficient. It is expected that any changes in these variables in the placebo group will reflect random variation only. Thus, these analyses will be restricted to the metformin group to overcome dilution of the potential correlations by individuals in the placebo group.

Exploratory analyses also will explore the correlation between baseline metabolite features and FWR-MRI, systemic hormones, and cytokines. These analyses will be restricted to

the metabolite features that are members of a common pathway to reduce the potential for an inflated alpha level.

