### **9.2 Sample Size Justification**

Our sample size ensures adequate power to test all primary specific aims. We assume an initial sample size of 75 women per arm and allow the possibility of up to 20% dropout for the 12-month follow-up measurement. This results in at least 60 evaluable women per group. To justify the sample size, we use the simplified comparison of change between 12 months versus baseline (ignoring the 6 month measurement). For the FWR-MRI-derived change in breast density, we will be able to detect a decrease of 0.516 standard deviation (SD) units in the metformin treated women with 80% statistical power, assuming a two-sided  $\alpha$  of 0.05. To estimate what this change would be in relation to breast density, we used the relationship between breast density and  $\log(\text{Fra50})$  based on our previous data. Based on an analysis of our cross-sectional data, the estimated SD of  $\log(\text{Fra50})$  is 2.40. Thus, a decrease of 0.516 SD units corresponds to a change of  $-1.2384$  ( $-0.516 \times 2.40$ ). Based on the regression line, this is equivalent to a 10% decrease in breast density as determined by standard mammography. For the additional primary outcomes (such as systemic hormones, cytokines, and weight), we will be able to detect a difference of 0.516 SD units with 80% statistical power, assuming a sample size of 60 evaluable women per group. Based on our previous experience, we anticipate that 65% of the proposed cohort will provide sufficient NAF for metabolomic analysis, which results in 39 women per group (allowing for up to 20% drop-out). This will allow us to detect a difference of 0.643 SD units with 80% statistical power.

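### Correlations between metabolite changes and marker changes are estimated in the metformin arm only, so ordinary co-variation can be misread as a metformin-induced link

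*Combined protocol and SAP*

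**What the plan says.** Section 9.1 (Analysis Plan, metabolomic aim) first compares the change in each metabolite between arms by t-test with q-values. As an exploratory step it then estimates Pearson correlations between metabolite changes and changes in FWR-MRI, body weight/composition, systemic hormones and cytokines. It justifies leaving out the placebo arm with "It is expected that any changes in these variables in the placebo group will reflect random variation only", and concludes that "these analyses will be restricted to the metformin group to overcome dilution of the potential correlations by individuals in the placebo group".

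The question being served is a secondary objective in Section 1: whether metabolic changes caused by metformin go along with marker changes or side effects caused by metformin. Section 2.3.3 gives the purpose as understanding mechanism, and the Schema lists correlations of metabolomic profiles with risk markers among the secondary endpoints.

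For these correlations the plan states no test, threshold, confidence interval or adjustment, and no placebo counterpart.

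**The concern.** Within one arm, a woman's change is the drug's effect on her plus everything else that happened to her over the year. A correlation of two such changes cannot say which part produced it.

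The stated justification does not close this gap. Changes can be random around zero in the placebo arm and still be strongly correlated with each other. The protocol itself points to shared sources of change that do not depend on the drug:

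- Section 2.3.2 ties leptin directly, and adiponectin inversely, to body fat, so weight drift can move several markers at once.
- Section 3 has diet and activity questionnaires completed again at month 12, to detect changes during the intervention.
- Sections 7.3 and 7.4 place the research visits in the midluteal phase only where feasible. The Schedule of Events puts blood, NAF and MRI at the same visits, so a phase mismatch can affect all of them together.

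What is at stake is the reading of the secondary metabolomic objective. A correlation that would appear equally under placebo could be taken as evidence of how metformin works.

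**Working it through.** **1. Inputs.** Section 9.2: "We assume an initial sample size of 75 women per arm and allow the possibility of up to 20% dropout"; "This results in at least 60 evaluable women per group". For NAF, 65% of these are expected to give enough fluid. The plan sizes plasma metabolomics nowhere separately, so 60 is used for it. Correlations with FWR-MRI may have fewer women, since those who cannot fit the scanner have no MRI. The two-sided 0.05 level is borrowed from the power calculation ("with 80% statistical power, assuming a two-sided" level of 0.05). The drug-unrelated correlation, rho, is an assumption, taken over 0.2 to 0.5.

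**2. The plan's own figures reproduce.** 75 × 0.80 = 60 and 60 × 0.65 = 39 per arm. The two-sample t-test at 80% power gives detectable differences of 0.5157 SD (n = 60) and 0.6426 SD (n = 39). These match "we will be able to detect a difference of 0.516 SD units with 80% statistical power" and "This will allow us to detect a difference of 0.643 SD units with 80% statistical power". They concern differences in means; no figure is given for the correlations.

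**3. What a one-arm correlation measures.** Write the metabolite change as X and the marker change as Y. Adding a constant drug shift to X, Y or both leaves their correlation within the arm unchanged. Two things follow.

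- Choosing metabolites because their mean differs between arms does not remove drug-unrelated co-variation.
- If metformin shifts both variables by the same amount in every woman and the remaining variation is independent, the metformin-arm correlation is about zero. In simulation (n = 60, shifts of 0.643 and 0.516 SD) it was significant in 5.0% of trials. The one-arm analysis can therefore miss a real effect as well as suggest a false one.

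**4. Size.** The correlation is nominally significant when |r| exceeds t/√(t² + n − 2), with t the 97.5% point on n − 2 degrees of freedom. That is 0.254 at n = 60 and 0.316 at n = 39. By Fisher's z, the chance of crossing it is about Φ(atanh(rho)·√(n − 3) − 1.96):

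- n = 60, rho 0.2: Φ(0.2027 × 7.550 − 1.96) = Φ(−0.43) = 33%
- n = 60, rho 0.3: Φ(0.3095 × 7.550 − 1.96) = Φ(0.38) = 65%
- n = 39, rho 0.2: Φ(0.2027 × 6 − 1.96) = Φ(−0.74) = 23%
- n = 39, rho 0.3: Φ(0.3095 × 6 − 1.96) = Φ(−0.10) = 46%

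A simulation checks this: 20,000 trials per setting, bivariate normal changes, the same rho in both arms, and a 0.643 SD metformin shift in the metabolite only.

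| n per arm | rho | Significant, metformin arm | Significant, placebo arm |
|---|---|---|---|
| 60 | 0.2 | 34% | 34% |
| 60 | 0.3 | 65% | 65% |
| 60 | 0.4 | 90% | 90% |
| 60 | 0.5 | 99% | 99% |
| 39 | 0.2 | 23% | 23% |
| 39 | 0.3 | 47% | 47% |
| 39 | 0.4 | 73% | 73% |
| 39 | 0.5 | 92% | 92% |

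The placebo column is what the plan does not look at.

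**5. Comparing the two correlations formally.** In all of these settings a Fisher-z comparison between arms is significant in about 5% of trials. If a correlation of 0.3 exists only under metformin, its power is 38% (n = 60) and 27% (n = 39).

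**6. Precision of a single correlation.** An observed r of 0.3 has the 95% interval tanh(0.3095 ± 1.96/√(n − 3)), which is 0.05 to 0.51 at n = 60 and −0.02 to 0.56 at n = 39.

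**The case against.** The strongest reply has four parts.

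- **The analysis is exploratory.** Section 9.1 says so and only proposes to estimate a correlation. The percentages above are not type I error: with a true within-arm correlation of 0.3, they are the power to detect an association that exists. An error arises only if the association is then read causally. This stands, and it limits the point to interpretation.
- **Placebo is used elsewhere.** Metabolite changes and marker changes are each compared between arms. The secondary FWR-MRI analyses adjust for weight, hormones and cytokines using both arms. This also stands: placebo is left out of this one step, not of the metabolomic aim.
- **Shared causes are partly controlled** by midluteal scheduling where feasible and by the diet and activity questionnaires. Partly true, but none of these is brought into the correlations.
- **Adding placebo would dilute the correlation.** That applies to pooling the arms. It does not apply to showing them separately.

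A reader might also see a contradiction with the mixed model, where "The time parameter tests if there is a change among placebo treated women". The documents do not support that. This is a standard model term for mean change, and one can test it while expecting no systematic change.

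Finally, a reader might conclude that every mechanistic statement should rest on an arm-by-metabolite-change interaction. That goes too far. The interaction tests effect modification. If metformin moves a metabolite that acts on the marker with the same slope in both arms, this is ordinary mediation, yet the interaction is null.

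**Conclusion.** The point holds as a gap in interpretation. Leaving out placebo rests on an assumption that would not justify the restriction even if placebo changes were random, because random changes can be correlated. At an assumed drug-unrelated correlation of 0.2 to 0.3, a nominally significant metformin-arm correlation appears in about 23% to 47% of trials at n = 39 and 33% to 65% at n = 60. Those figures depend on the assumed correlation, on bivariate normal changes, and on a 0.05 threshold that the plan does not set for this analysis.

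A reader might infer that natural co-variation will be reported as a metformin mechanism. The documents do not support that: they contain no rule turning a correlation into a mechanistic claim, and no estimate of the natural correlation. What they support is that it can be misread that way, and that the planned output gives no means of noticing. The primary breast density comparison and the between-arm metabolite tests are untouched.

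**What to change.** In Section 9.1:

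1. Estimate the same correlations, with confidence intervals, in both arms and report them side by side.
2. Delete the sentence assuming that placebo changes are only random. If that expectation also means no co-variation, the placebo correlations will be near zero and will show it.
3. State that a metformin-arm correlation will not be called metformin-induced on its own. It is to be read with the placebo correlation and with the between-arm comparisons of mean change in that metabolite and that marker.
4. If wanted, report an arm-by-metabolite-change interaction as a descriptive supplement, with its low power and its blindness to equal-slope mediation noted. Do not make it the required basis for a mechanistic statement.

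The cost is a few lines of SAP text and one more set of correlations on data already collected. The intervals will be wide, especially for NAF, so many pairs will remain inconclusive.

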### **9.2 Sample Size Justification**

Our sample size ensures adequate power to test all primary specific aims. We assume an initial sample size of 75 women per arm and allow the possibility of up to 20% dropout for the 12-month follow-up measurement. This results in at least 60 evaluable women per group. To justify the sample size, we use the simplified comparison of change between 12 months versus baseline (ignoring the 6 month measurement). For the FWR-MRI-derived change in breast density, we will be able to detect a decrease of 0.516 standard deviation (SD) units in the metformin treated women with 80% statistical power, assuming a two-sided  $\alpha$  of 0.05. To estimate what this change would be in relation to breast density, we used the relationship between breast density and  $\log(\text{Fra50})$  based on our previous data. Based on an analysis of our cross-sectional data, the estimated SD of  $\log(\text{Fra50})$  is 2.40. Thus, a decrease of 0.516 SD units corresponds to a change of  $-1.2384$  ( $-0.516 \times 2.40$ ). Based on the regression line, this is equivalent to a 10% decrease in breast density as determined by standard mammography. For the additional primary outcomes (such as systemic hormones, cytokines, and weight), we will be able to detect a difference of 0.516 SD units with 80% statistical power, assuming a sample size of 60 evaluable women per group. Based on our previous experience, we anticipate that 65% of the proposed cohort will provide sufficient NAF for metabolomic analysis, which results in 39 women per group (allowing for up to 20% drop-out). This will allow us to detect a difference of 0.643 SD units with 80% statistical power.

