## **3. SUMMARY OF STUDY PLAN**

This is a Phase II double-blind, randomized, placebo-controlled trial of metformin to determine its potential effects on recognized and putative markers of breast cancer risk in overweight or obese premenopausal women who have metabolic syndrome. The study endpoints are modulation of breast density and metabolic disturbances, risk factors associated with breast cancer. In addition, the study will explore the application of metabolomics as a systems biology approach to assess the chemopreventive mechanisms of metformin and to understand factors affecting markers of breast cancer risk. The study will also explore the effect of metformin intervention on tissue architecture as well as cellular and molecular targets in breast tissue collected in a subgroup of participants.

At the consenting/screening visit, participants will sign informed consent and undergo the following procedures for screening: collection of medical history and medication usage history, demographic information (age, race/ethnicity), anthropometric measurements (weight (wt), height, waist circumference, waist-hip ratio), breast cancer risk information (family and personal history of breast cancer, age at menarche, parity, and prior breast biopsy), information on menstrual patterns/cycles, and a fasting blood sample for complete blood count with differential (CBC/w diff) and comprehensive metabolic panel (CMP).

Participants who meet all selection criteria will return in the midluteal phase of the menstrual cycle, when feasible, to undergo baseline evaluation including collection of a fasting blood for research biomarkers, collection of NAF for metabolomic analysis, MRI assessment of breast density, collection of wt, waist circumference, and waist-hip ratio measurements, and the optional core needle biopsy for breast tissue collection. Women who cannot fit into the MRI scanner due to the large body size will continue the study and undergo all other study procedures. Participants will also complete the Arizona Food Frequency Questionnaire (AFFQ) to measure usual dietary intake and the Arizona Activity Frequency Questionnaire (AAFQ) to assess usual physical activity.

Following completion of baseline evaluation, participants will be randomized to receive metformin or placebo for 12 months. We plan to randomize 150 eligible participants (75 per arm). With an anticipated attrition rate of 20% or less, we expect to have at least 60 women per

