arm completing the intervention. Participants will be asked to take one 850 mg metformin or one placebo tablet daily with a meal for the first four weeks, then two 850 mg metformin or two placebo tablets daily with meals for the remainder of the study. The same starting dose and gradual dose escalation up to 2,000 mg per day is used to minimize gastrointestinal symptoms for glycemic control in diabetics (GLUCOPHAGE® prescribing information).

Participants will be asked to keep an adverse event diary and menstrual calendar throughout the study. In addition, participants will be provided with an intake calendar for recording medication usage. Study personnel will contact study participants within a week after study agent has been initiated and within a week following scheduled dose increase to assess compliance and any potential problems. Participants will return to the clinic at months 3, 6, and 9 after initiation of agent intervention to undergo safety and compliance evaluation. For the month 6 visit, participants will be scheduled to return to the clinic in the midluteal phase of the menstrual cycle, when feasible. In addition to undergoing study procedures described above, participants will undergo wt, waist circumference, and waist-hip ratio measurements, have a fasting blood and NAF collected for research biomarkers, undergo MRI assessment of the breast if MRI was performed at the baseline visit, return unused pills and receive a new supply of study medication, and undergo the optional core needle biopsy. Study personnel will contact study participants at least once and as needed between clinic visits to assess compliance and any potential problems.

At the end of the 12-month agent intervention, participants will return to the clinic in the midluteal phase of the menstrual cycle, when feasible, to collect wt, waist circumference, and waist-hip ratio measurements, return unused drugs, review side effects, and have a fasting blood sample collected for safety labs and research biomarkers. Participant will also undergo NAF collection for metabolomics, and MRI assessment of the breast if MRI was performed at the baseline visit. Participants will also complete the AFFQ and AAFQ to assess any changes in dietary intake and physical activity during the intervention. Following the study intervention, participants will be followed for 2 weeks for any adverse reactions.

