## 4. PARTICIPANT SELECTION

### 4.1 Inclusion Criteria

- Premenopausal women
- 21-54 years of age
- No change in menstrual patterns for the past 6 months preceding the time of registration
- Have a BMI of 25 kg/m^2 or greater
- Large waist circumference
  - ≥ 88 cm (≥35 inches) or
  - ≥ 80 cm (≥31 inches) for Asian Americans, individuals with polycystic ovary syndrome, or individuals with non-alcoholic fatty liver disease
- Have at least one other component of metabolic syndrome (103) reported below:
  - Elevated triglycerides (≥ 150 mg/dL (1.7 mmol/L)) or on drug treatment for elevated triglycerides
  - Reduced HDL-C (< 50 mg/dL (1.3 mmol/L)) or on drug treatment for reduced HDL-C
  - Elevated blood pressure (≥ 130 mm Hg systolic blood pressure or ≥85 mm Hg diastolic blood pressure) or on antihypertensive drug treatment in a patient with a history of hypertension
  - Elevated fasting glucose (≥100 mg/dL)

- Mammogram negative for breast cancer within the 12 months preceding the time of registration for women  $\geq 50$  years of age
- Ability to understand and the willingness to sign a written informed consent document

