#### **4.2 Exclusion Criteria**

- Postmenopausal women
  - Amenorrhea for at least 12 months (preceding the time of registration), or
  - History of hysterectomy and bilateral salpingo-oophorectomy, or
  - At least 55 years of age with prior hysterectomy with or without oophorectomy, or
  - Age 35 to 54 with a prior hysterectomy without oophorectomy OR with a status of ovaries unknown with documented follicle-stimulating hormone level demonstrating elevation in postmenopausal range
- Women who are pregnant, planning pregnancy within the next year, or lactating/breastfeeding
- On treatment with any drug for diabetes
- Have uncontrolled intercurrent illness including, but not limited to, ongoing or active infection, symptomatic congestive heart failure, unstable angina pectoris, cardiac arrhythmia, or any illness that would limit compliance with study requirements
- Have received chemotherapy and/or radiation for any malignancy (excluding non-melanoma skin cancer and cancers confined to organs with removal as only treatment) in the past 5 years (preceding the time of registration)
- Have received other investigational agents within the past 3 months (preceding the time of registration)
- Have a history of lactic acidosis or risk factors for lactic acidosis
- Have renal disease or dysfunction (creatinine  $\geq 1.4$  mg/dL)
- Have hepatic dysfunction (bilirubin  $> 1.5$  x ULN unless with Gilberts syndrome or AST/ALT  $> 3$  x ULN)
- Have a history of alcoholism or high alcohol consumption (average of  $> 3$  standard drinks/day)
- Have a history of allergic reactions to metformin or similar drugs
- Have a history of severe claustrophobia
- Have electrically, magnetically, or mechanically activated implants including cardiac pacemaker, cochlear implants, magnetic surgical clips or prostheses
- Have breast implants

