## **7.3 Evaluations During Study Intervention**

Participants who meet all selection criteria will undergo the following baseline procedures. When feasible, these procedures will be scheduled in the midluteal phase of the menstrual cycle.

- Anthropometric measurements including wt, waist circumference, waist-hip ratio.
- A fasting blood for research biomarkers.
- Collection of urine for urine pregnancy test and research tests.
- Vital signs.
- Update information on menstrual patterns/cycles.
- Update medication usage.
- Completion of the Arizona Food Frequency Questionnaire (AFFQ) to measure usual dietary intake and the Arizona Activity Frequency Questionnaire (AAFQ) to assess usual physical activity.
- Nipple aspirate fluid, for those who are able to produce NAF, for metabolomic analysis. Breasts will be warmed and massaged. Nipple fluid will be aspirated by a hand-held aspirator.

- MRI assessment of breast density. All MRI images will be acquired on a 3T MRI scanner located in the department of Radiology of the University of Arizona Medical center. Fat-water imaging will be performed using the radial Gradient-Echo and Spin-Echo (GRASE) technique developed by co-investigator, [name] (114). Women who cannot fit into the MRI scanner due to the large body size will continue the study and undergo all other study procedures.
- Optional core needle biopsy. For participants who consent to this optional procedure, the medical specialist will use a 14-gauge needle under the ultrasound guidance to obtain up to 8 tissue cores from one of the breasts.

Following completion of baseline evaluation, participants will be randomized to receive metformin or placebo for 12 months. Participants will receive a supply of study medication. Participants will be asked to take one 850 mg metformin or one placebo tablet daily with a full 8 oz glass of water with a meal for the first four weeks, then two 850 mg metformin or two placebo tablets daily with meals for the remainder of the study. The same starting dose and gradual dose escalation up to 2,000 mg per day is used to minimize gastrointestinal symptoms for glycemic control in diabetics (GLUCOPHAGE® prescribing information).

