Participants will be asked to keep an adverse event diary and menstrual calendar throughout the study. In addition, participants will be provided with an intake calendar for recording medication usage. Study personnel will contact study participants within a week after study agent has been initiated and within a week following scheduled dose increase to assess compliance and any potential problems.

Participants will return to the clinic at month 3 ( $13 \pm 2$  wks) to undergo the following procedures:

- Collection of urine for urine pregnancy test.
- Vital signs.
- Update information on menstrual cycles.
- Update medication usage.
- Side effect evaluation.

Participants will return at month 6 ( $26 \pm 4$  wks) to undergo the following procedures:

- Collection of urine for urine pregnancy test and research tests.
- Vital signs.
- Update information on menstrual patterns/cycles.
- Update medication usage.
- Side effect evaluation.
- Return unused pills.
- Receive a new supply of study medication.
- Collection of wt, waist circumference, waist-hip ratio measurements.
- Collection of a fasting blood and NAF sample for research biomarkers.
- MRI assessment of the breast. Women who cannot fit into the MRI scanner due to the large body size will not undergo the MRI assessment.
- Optional breast core biopsy.

When feasible, the month 6 procedures will be scheduled in the midluteal phase of the menstrual cycle.

Participants will return to the clinic at month 9 ( $39 \pm 2$  wks) after initiation of agent intervention to undergo the following procedures:

- Collection of urine for urine pregnancy test.
- Vital signs.
- Update information on menstrual patterns/cycles.
- Update medication usage.
- Side effect evaluation.

Study personnel will contact study participants at least once and as needed between clinic visits to assess compliance and any potential problems.

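### Section 9.2 takes 60 evaluable women per group for the MRI primary endpoint from dropout alone, with no allowance for randomised women who cannot be scanned

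*Combined protocol and SAP*

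**What the plan says.** Section 9.2 starts from 75 women per arm, allows up to 20% dropout at 12 months, and concludes: "This results in at least 60 evaluable women per group". It sizes on a simplified comparison of the change from baseline to month 12, leaving out month 6. For breast density it claims 80% power to detect 0.516 SD at two-sided 0.05. The same 60 and the same 0.516 SD are then given for hormones, cytokines and weight. For nipple aspirate fluid (NAF) the same paragraph applies an extra availability factor of 65%, which gives 39 per group and 0.643 SD.

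Section 3 says: "Women who cannot fit into the MRI scanner due to the large body size will continue the study and undergo all other study procedures". Footnote 3 of the schedule in Section 7.1 and the baseline list in Section 7.3 repeat this. Section 3 makes the later scans conditional: "MRI assessment of the breast if MRI was performed at the baseline visit". For months 6 and 12, Sections 7.3 and 7.4 say: "Women who cannot fit into the MRI scanner due to the large body size will not undergo the MRI assessment".

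Randomisation comes after the baseline work-up: "Following completion of baseline evaluation, participants will be randomized to receive metformin or placebo for 12 months". No passage makes a completed scan a condition. Section 4.1 sets a lower BMI limit only ("Have a BMI of 25 kg/m 2 or greater"). Section 4.2 excludes some women who could not be scanned ("Have a history of severe claustrophobia", and certain implants), but has no criterion for body size.

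The planned analysis is in Section 9.1: "Analysis for all study endpoints will be based on a linear mixed-effects model for the observed values across time".

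**The concern.** The 60 counts women who complete the trial, whereas the primary comparison needs women with MRI at both baseline and month 12. The protocol foresees that these groups can differ and states the rule several times, but the sample size does not carry it through.

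The 20% cannot be read as already covering unscannable women. Section 3 describes it as attrition and the resulting 60 as women who complete the intervention, which unscannable women can do. Section 9.2 also applies the same 60 to weight and hormones, which these women do provide.

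At stake are the number, power and detectable difference stated for the primary endpoint. They assume that every completer has been scanned, and a reader of 9.2 cannot see that assumption or judge its size.

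**Working it through.** **Inputs from the documents.** 75 randomised per arm (Sections 3 and 9.2); dropout up to 20%, two-sided 0.05, 80% power, 0.516 SD (Section 9.2); NAF availability 65% (Section 9.2).

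**Input not in the documents.** The unscannable share u. The values below (2%, 5%, 10%) are assumptions chosen to show a range.

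**Step 1: reproduce the plan.** 75 × (1 − 0.20) = 60. A two-sample t-test (noncentral t) with 60 per arm has 80.04% power at 0.516 SD, and its detectable difference at 80% power is 0.5157 SD. For NAF, 60 × 0.65 = 39, which gives 0.643 SD. All the stated figures reproduce. They leave no margin: 75 × 0.80 is exactly 60, and 60 gives almost exactly 80%.

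**Step 2: add the missing factor.** MRI n per arm = 75 × (1 − dropout) × (1 − u). At 20% dropout this is 60 × (1 − u), which is below 60 for any u above zero.

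| Assumed u | MRI n per arm | Power at 0.516 SD | Detectable difference at 80% power |
|---|---|---|---|
| 0% | 60 | 80.0% | 0.516 SD |
| 2% | 58.8 | 79.2% | 0.521 SD |
| 5% | 57 | 78.0% | 0.529 SD |
| 10% | 54 | 75.7% | 0.544 SD |

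**Step 3: how much lower dropout would restore 60.** Setting 75 × (1 − dropout) × (1 − u) = 60 gives a maximum dropout of 1 − 60 / [75 × (1 − u)]. This is 18.4% at u = 2%, 15.8% at u = 5% and 11.1% at u = 10%.

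**Step 4: what the mixed model could recover.** A scanned woman who drops out still contributes her baseline scan and any month-6 scan. A woman never scanned contributes nothing to this endpoint. I assumed compound symmetry, data missing at random, 20% dropout, a within-woman correlation of 0.5 to 0.9, and anything from none to all of the dropouts having a month-6 scan. For the 12-month-minus-baseline contrast, the effective number per arm is 2(1 − correlation) divided by the per-arm variance of that contrast, with each scan's variance set to 1. It is 60.6–64.3 at u = 0, 59.4–63.0 at 2%, 57.6–61.1 at 5% and 54.5–57.9 at 10%. On this contrast the model has a little slack, which is used up at a share between 1.0% and 6.7%, depending on the assumptions.

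**The case against.** The best case for leaving 9.2 alone has three parts.

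- **The scanner rule is only a contingency.** No count is given, the true share may be near zero, and 20% is a ceiling on dropout. This stands. It makes the shortfall conditional, but does not supply the missing assumption.
- **The effect is small at modest shares.** At 5%, power falls by about two points and the detectable difference rises from 0.516 to 0.529 SD. This also stands.
- **9.2 is openly a simplification, and the planned model uses more data.** This stands in part, as step 4 shows.

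Two stronger readings are tempting, and the documents support neither.

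- **A reader might infer that a share of 10% or more must leave the planned analysis underpowered.** On the 12-month contrast, power at 10% is indeed 76.1% to 78.6% under the step 4 assumptions. But Section 9.1 plans a group-by-time interaction over 0, 6 and 12 months and does not reduce it to that contrast. A large-sample joint test of the interaction, at a 10% share, has about 80% to 87% power if the full 0.516 SD effect is already present at month 6. If the effect grows linearly, it has about 67% to 70%, but then only 72% to 75% with nobody unscannable. The shape of the effect matters more than the share.
- **A reader might scale up the 10% density decrease quoted in 9.2.** That figure rests on an SD of 2.40 from cross-sectional data. With equal variance at both visits, the SD of a change is 2.40 × √[2(1 − correlation)], which equals 2.40 only at a correlation of 0.5. The documents give no correlation, so I restate nothing in density units.

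**Conclusion.** The omission is real and the arithmetic is certain; the severity is minor. On 9.2's own comparison at 20% dropout, the stated 60 holds for MRI only if no completer was unscannable. At assumed shares of 2% to 10%, the loss is 1.2 to 6 women per arm and about 1 to 4 points of power.

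The actual size depends on a share that the documents do not give. At 5% or below it is small, and dropout of 15.8% or less (at 5%), or month-6 scans in the mixed model, may offset it. This is a defect in the stated justification. It does not show that the trial is too small or that the primary analysis will fail.

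**What to change.** In Section 9.2:

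1. State an assumed MRI-evaluable share. Either label it as an assumption with a range, or take it from the pooled, blinded count of baseline scans not obtained, which needs no unblinding.
2. Compute MRI n = 75 × (1 − dropout) × (1 − unscannable share), in the same way as the NAF number.
3. Restate the MRI number and the detectable difference or power for breast density, in SD units. At an assumed 5% this would be 57 per group, with 0.529 SD detectable at 80% power, or 78.0% power at 0.516 SD.
4. Keep 60 and 0.516 SD for the blood and anthropometric endpoints.

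The cost is two or three sentences and a slightly less favourable stated figure for the primary endpoint. It needs no extra participants or procedures, and no change to randomisation or to the planned model.
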